#### **6.2.5    Rate of Use of Immunomodulatory Agents**

The use of other immunomodulatory agents as treatment for COVID-19, such as corticosteroids, tocilizumab, anakinra, or eculizumab, will be assessed as a secondary endpoint. These medications will be identified on the CRF as concomitant medications and defined by groups of certain WHODD preferred names. The list of WHODD terms is provided in [Appendix 1](#).

A patient will be considered to have used an immunomodulatory agent if any medication used by the patient between Day 1 and Day 28 is coded to the list of preferred names in [Appendix 1](#).

The rate of use of immunomodulatory agents will be calculated as:

- $$\frac{\text{(Number of patients using an immunomodulatory agent between Day 1 and Day 28)}}{\text{(Number of patients in the ITT population)}}$$

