#### Secondary Efficacy Endpoints

1. The number of ventilator-free days, defined as the number of days that patients are alive and not intubated, from randomization to Day 28
2. The 28-day mortality rate, defined as the proportion of patients with outcome of death during the 28 days following randomization
3. The 15-day mortality rate, defined as the proportion of patients with outcome of death during the 15 days following randomization
4. The time to improvement by at least 2 points relative to Baseline on the 7-point ordinal scale of clinical status
5. The clinical status as assessed by the 7-point ordinal scale of clinical status at Days 8, 15, 22, and 28
6. The rate of use of immunomodulatory agents as treatment for COVID-19 is defined as the proportion of patients reporting use of medications such as corticosteroids, tocilizumab, anakinra, or eculizumab as treatment for COVID-19, during 28 days following randomization.

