## **Secondary Endpoints**

1. The number of ventilator-free days, defined as the number of days that patients are alive and not intubated, from randomization to Day 28
2. The mortality rate at Day 28 is defined as the number of patients with outcome of death during the 28 days following randomization divided by the total number of patients in the ITT population
3. The mortality rate at Day 15 is defined as the number of patients with outcome of death in the 15 days following randomization divided by the total number of patients in the ITT population.
4. The time to improvement by at least 2 points relative to Baseline on the 7-point ordinal scale of clinical status. All enrolled patients will have a score between 3 and 5 by virtue of being hospitalized and non-intubated; therefore, patients who progress from 3 to 1, from 4 to 2, or from 5 to 3 will have met the definition of improvement.
5. The clinical status as assessed by the 7-point ordinal scale of clinical status at Days 8, 15, 22, and 28.
6. The rate of use of immunomodulatory agents as treatment for COVID-19 is defined as the proportion of patients reporting use of medications such as corticosteroids, tocilizumab, anakinra, or eculizumab as treatment for COVID-19, during 28 days following randomization divided by the patients in the ITT population.

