#### 7.4.2.5 Use of Immunomodulatory Agents

The rate of use of immunomodulatory agents as treatment for COVID-19 will be compared between treatment arms using the CMH test stratified by age (< 60 years versus  $\geq 60$  years) and baseline 7-point clinical status scale (baseline 3 or 4 versus 5). The point estimates and 95% confidence intervals of the rates of immunomodulatory agents use will be presented by treatment arm. The CMH odds ratio, difference in rates of immunomodulatory agent use, and associated 95% confidence intervals will be presented.

In addition, the number of immunomodulatory agents will be summarized using descriptive statistics (e.g. number of immunomodulatory agents used per patient). Additional summaries presenting the percentage of patients using immunomodulatory agents in each defined category in [Appendix 1](#) and the immunomodulatory agents summarized by preferred term may be generated.

Immunomodulatory agents used will be listed by patient.

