## 11 APPENDIX 1: IMMUNOMODULATORY AGENTS

Immunomodulatory agent usage will be identified based on concomitant medications that are classified according to the following WHODD preferred names.

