**Table 8 MedDRA Preferred Term List for Immunomodulatory Agents**

Immunomodulatory Agent Category	Preferred Names(s)*
Corticosteroids	Decadron, Dexamethason, Hydrocortisone, Metholprednisolne, Prednisone, Solumedrol
IL-6 inhibitors	Tocilizumab
IL-1 inhibitors	Anakinra
Antiretrovirals	Remdesivir

\*WHO-DDE B3, March, 2020.

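### SAP Table 8, the fixed list behind a CMH-tested secondary endpoint, counts remdesivir as an immunomodulatory agent and leaves out eculizumab, which the endpoint names

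*SAP*

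**What the plan says.** The protocol synopsis (secondary efficacy endpoint 6) defines the endpoint as the "proportion of patients reporting use of medications such as corticosteroids, tocilizumab, anakinra, or eculizumab as treatment for COVID-19", over the 28 days after randomization. Protocol 11.1.1 repeats the definition, again with "medications such as corticosteroids, tocilizumab, anakinra, or eculizumab as treatment for COVID-19". The opening sentence of SAP 6.2.5 names the same four: use of agents "such as corticosteroids, tocilizumab, anakinra, or eculizumab, will be assessed as a secondary endpoint".

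SAP 6.2.5 then gives the counting rule. A patient is "considered to have used an immunomodulatory agent if any medication used by the patient between Day 1 and Day 28 is coded to" the Appendix 1 list. Appendix 1 says that usage is identified from concomitant medications "classified according to the following WHODD preferred names". Neither place has a category for other agents or a review step for unlisted drugs.

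Table 8 has four categories: six corticosteroid names, IL-6 inhibitors (tocilizumab only), IL-1 inhibitors (anakinra only), and "Antiretrovirals" (remdesivir only). Eculizumab does not appear.

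SAP 7.4.2.5 tests the result: "The rate of use of immunomodulatory agents as treatment for COVID-19 will be compared between treatment arms using the CMH test", stratified by age and baseline clinical status, with an odds ratio and a rate difference. SAP section 9 states that nothing departs from the protocol's analysis.

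**The concern.** The endpoint text is illustrative, but the counting rule makes Table 8 decisive, and the table departs from the endpoint in both directions. It adds a drug under a heading that is not an immunomodulator class, and it drops an agent that the endpoint names. The tested quantity is then not the one the objective describes.

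Counting remdesivir-only patients as users raises both arms' rates. If such use is equal between arms, it shrinks a real difference; if it is unequal, it can create a difference where none exists. Omitting an agent pulls the rate down in whichever arm used it.

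Two smaller mismatches belong to the same edit. Table 8 also lacks sarilumab and canakinumab, which Protocol 4.1.2 (item 20) and 6.6 give as examples of IL-1 or IL-6 blocking immunomodulators, although the endpoint does not name them. The counting sentence and formula in SAP 6.2.5 also omit the condition that the drug be given to treat COVID-19, which the opening sentence of 6.2.5 and section 7.4.2.5 both carry.

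**Working it through.** **Comparison of the texts**

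| Agent or class | Named in endpoint (Protocol 11.1.1, SAP 6.2.5) | In SAP Table 8 |
|---|---|---|
| Corticosteroids | yes | yes |
| Tocilizumab | yes | yes |
| Anakinra | yes | yes |
| Eculizumab | yes | **no** |
| Remdesivir | no | **yes** |
| Sarilumab, canakinumab | no (named in Protocol 4.1.2 and 6.6) | no |

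Three of the four named agents or classes are in the table. One of the table's four categories has no counterpart in the endpoint. Protocol 6.6 names antiviral agents separately from the IL-1/IL-6 immunomodulators.

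**Inputs.** SAP 3.4 plans about 200 patients at 1:1, so 200/2 = 100 per arm and one patient is 1 percentage point of that arm's rate. That sample size is for the primary endpoint. It reproduces at 100 per arm for 13.5% vs 26.5%, one-sided 0.10, 80% power, with a continuity correction. The documents give no expected rates, power or alpha for immunomodulatory use, so everything below rests on assumed rates.

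**Effect of counting remdesivir.** Let r be the true rate of use and q0 the share of patients with no listed immunomodulator who take remdesivir.

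- Observed rate = r + (1 − r)·q0.
- With q0 equal in both arms, observed difference = (1 − q0)·(r2 − r1). Remdesivir use need not be independent of other use.

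Assume true rates of 40% vs 55%, 100 per arm, and an unstratified two-proportion test (normal approximation, pooled variance) at one-sided 0.10, a level borrowed from the primary endpoint:

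| q0 | Observed rates | Difference (points) | Power |
|---|---|---|---|
| 0% | 40.0 vs 55.0% | 15.0 | 80% |
| 10% | 46.0 vs 59.5% | 13.5 | 74% |
| 20% | 52.0 vs 64.0% | 12.0 | 67% |
| 30% | 58.0 vs 68.5% | 10.5 | 60% |
| 50% | 70.0 vs 77.5% | 7.5 | 47% |

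The loss depends on the base rates. Going from q0 = 0 to 30%, power falls from 87% to 58% for 20% vs 35%, from 84% to 69% for 60% vs 75%, and from 98% to 92% for 80% vs 95%.

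**Unequal remdesivir use.** If true rates are equal and q0 differs by 10 points between arms, the false difference is (1 − r) × 10 points: 6 points at r = 40% and 2 points at r = 80%.

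**Lower bound.** If every remdesivir patient also takes a listed immunomodulator, q0 = 0 and including remdesivir causes no error.

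**Effect of an omitted agent.** If m patients per 100 use only an omitted agent, that arm's rate falls by m points. With 2 such patients in one arm and 5 in the other, the difference shifts by 5 − 2 = 3 points.

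**The case against.** The best defence is that the endpoint list is introduced as a set of examples, the protocol leaves analysis details to the SAP, and the stratified CMH method is unchanged. On that view Table 8 only fills in an open list. Remdesivir appears nowhere else in the documents, and SAP 7.2.4 mentions immunomodulatory agents and antivirals together, so the inclusion may be deliberate. This stands in part: a deliberate inclusion is possible, but no reason is given. An open list also cannot explain dropping an agent that it names.

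The second defence is visibility. SAP 7.2.4 requires concomitant medications to be summarized by ATC level and preferred term, with those of special interest summarized separately and listed. SAP 7.4.2.5 requires a by-patient listing of immunomodulatory agents and allows the "percentage of patients using immunomodulatory agents in each defined category in" Appendix 1. A reader could therefore find remdesivir-only patients, and use of an omitted agent would show in the 7.2.4 tables. This stands, but none of these outputs changes the tested rate, and the optional category summaries have no row for an omitted agent.

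Third, the sizes are hypothetical and power would suffer less if use is high in both arms, as the 80% vs 95% case shows. That stands. So does the point that SAP 6.2.5 can be read as carrying the COVID-19 condition from its opening sentence into the counting rule; that mismatch is loose drafting more than contradiction. Sarilumab and canakinumab are a matter of consistency only.

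**Conclusion.** The concern holds. Table 8 is the operative list for a between-arm test, it includes remdesivir without explanation, and it omits an agent named in the endpoint wording of both documents, with no declared change. These are facts of the text and need no assumption.

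The size is uncertain because the documents give no usage rates. With equal remdesivir use among otherwise non-using patients, a true difference shrinks by the factor (1 − q0), which ranges from no effect at q0 = 0 to half at q0 = 50%. The effect of the omission is 1 point per affected patient per 100 and may be very small. The damage is confined to one of six secondary efficacy endpoints; the primary analysis and the sample size are untouched. It should be fixed because the correction is nearly free before unblinding and would look data-driven afterwards.

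**What to change.** Before unblinding:

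1. Remove remdesivir from Table 8 and leave antivirals to the concomitant-medication summaries in SAP 7.2.4. If it is kept on purpose, state why and declare it in SAP section 9.
2. Add eculizumab to Table 8.
3. For consistency with Protocol 6.6, also add sarilumab and canakinumab.
4. Carry the COVID-19 treatment condition into the counting sentence and formula of SAP 6.2.5, applied where indication is recorded. The documents do not say whether it is.
5. In the same edit, check the listed names against WHODD. The table title refers to MedDRA terms, while 6.2.5 and Appendix 1 refer to WHODD names.

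Keep the count as any use within the 28 days, as the protocol defines it.

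The cost is an edit to one appendix table and to one sentence and one formula in SAP 6.2.5. The list changes need no new data, because concomitant medications are already collected and coded. Item 4 can be applied only if the CRF captures indication.

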## 4 PATIENT SELECTION AND WITHDRAWAL

### 4.1 Target Population

#### 4.1.1 *Inclusion Criteria*

1. Hospitalized or will be hospitalized prior to randomization for the treatment of severe COVID-19 with SARS-CoV-2 infection confirmed by either a) a positive reverse transcriptase polymerase chain reaction (RT-PCR) or b) an antigen-based test from any respiratory, nasopharyngeal, saliva, blood, or stool specimen at Screening or documented within 1 week prior to the start of Screening (Severe COVID-19 is defined as confirmed disease in patients who are hospitalized with hypoxia [ $\text{SpO}_2 \leq 93\%$  on room air], respiratory rate  $>30$ ,  $\text{PaO}_2/\text{FiO}_2 <300$ , but do not require IMV).
2. Age  $\geq 18$  years
3. Platelet count  $\geq 50,000/\mu\text{L}$
4. If fertile, willing to use effective birth control methods during the study
5. Provision of informed consent within 96 hours after hospitalization

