#### **4.1.2     *Exclusion Criteria***

1. In the opinion of the investigator, progression to death is imminent and inevitable within the next 24 hours, irrespective of the provision of treatments
2. Currently intubated or intubated between screening and randomization
3. Suspected active uncontrolled bacterial, fungal, viral, or other infection (besides COVID-19)
4. Prior allogenic hematopoietic stem cell transplantation
5. Active lung cancer or history of lung cancer within the past 12 months
6. Any active grade 2 or higher hemorrhage
7. Any active gastrointestinal or metabolic condition that could interfere with absorption of oral medication
8. Uncontrolled intercurrent illness that, in the judgment of the treating physician, would limit compliance with study requirements
9. Known seropositivity for human immunodeficiency virus with CD4 count < 200/mm^3 within 3 months prior to randomization
10. Pregnant or breastfeeding, or positive pregnancy test in a pre-dose examination
11. Concurrent enrollment in another interventional trial (investigational COVID-19 antiviral studies are permitted)
12. Serum creatinine > 2.5 mg/dL
13. Total bilirubin > 4× the upper limit of normal
14. QT corrected by the Fridericia method (QTcF) prolongation > 480 msec
15. Known history of New York Heart Association Class II, III, or IV congestive heart failure prior to hospital admission
16. Known allergic reaction to any JAK2 inhibitor
17. Exposure to any JAK2 inhibitor within 28 days
18. Currently receiving a strong CYP3A4 inhibitor or strong P450 inducer ([Appendix 1](#) and [Appendix 2](#), respectively) and unable to stop the medication prior to the first dose of study drug and throughout the duration of study drug administration
19. Treatment with cytoreductive chemotherapy administered within 14 days prior to randomization

20. Administration of an IL-1 or IL-6 blocking immunomodulatory agent (such as tocilizumab, canakinumab, sarilumab, anakinra) within 48 hours prior to randomization
21. Currently receiving therapeutic anticoagulation or anti-platelet medication and unable to stop the medication prior to randomization. Prophylactic anticoagulation therapy or aspirin ( $\leq 100$ mg) are permitted.
22. Unable to ingest capsules or tablets at randomization

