## 6.6 Concomitant and Excluded Therapies

Treatment with cytoreductive therapy is not permitted during the assigned treatment period. Pacritinib is metabolized by the P450 system, including cytochrome P450 3A4 (CYP3A4). Use of strong CYP3A4 inhibitors is not permitted as these can lead to significantly increased concentrations of pacritinib. Use of strong cytochrome P450 (CYP450) inducers is not permitted as these can lead to significantly reduced concentrations of pacritinib. Lists of selected strong CYP3A4 inhibitors and P450 inducers are found in [Appendix 1](#) and [Appendix 2](#), respectively.

Concomitant use of investigational agents (those administered as part of a clinical trial) for the treatment of COVID-19 is prohibited with the exception of antiviral agents. The use of IL-1 or IL-6 blocking immunomodulatory agents (such as tocilizumab, canakinumab, sarilumab, anakinra) is allowed if, in the opinion of the investigator, a patient is clinically deteriorating. However, patients who require IL-1 or IL-6 blocking agents must be discontinued from study drug. Hydroxychloroquine, chloroquine, azithromycin, corticosteroids, and antiviral agents are permitted concomitant medications.

Electrolyte repletion should be considered for patients who have electrolyte levels below the lower limit of normal upon entry into the study or while receiving pacritinib/placebo.

Patients who develop worsening gastrointestinal symptoms with the initiation of pacritinib/placebo treatment may be treated with standard antidiarrheal and/or anti-emetic medications (Section [6.6.1](#)).

Treatment-dose anticoagulation and anti-platelet therapy may be administered after randomization, if required; patients do not need to discontinue pacritinib/placebo if one of these medications is initiated. However, patients should not receive such agents concomitant with study drug administration if their platelet counts drop to < 50,000/ $\mu$ L; prophylaxis-dose anticoagulants are permitted for all patients on study. Treatment-dose anticoagulants and anti-platelet agents may be administered at any dose after the study drug treatment period has ended.

Cytotoxic chemotherapy or cancer-directed immunotherapy is prohibited during the pacritinib/placebo treatment period (14 or 21 days). Cancer-directed immunotherapy includes immune checkpoint inhibitors, antibody-based cancer therapy, and cell-based cancer therapy.

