### 2.2 Secondary Objectives

1. To compare the number of ventilator-free days, defined as the number of days that patients are alive and not intubated, from randomization to Day 28 between pacritinib + SOC versus placebo + SOC
2. To compare the mortality rate between pacritinib + SOC versus placebo + SOC at Day 28
3. To compare the mortality rate between pacritinib + SOC versus placebo + SOC at Day 15
4. To compare the time to improvement by at least 2 points relative to Baseline on the 7-point ordinal scale of clinical status between pacritinib + SOC versus placebo + SOC
5. To compare the clinical status assessed by the 7-point ordinal scale of clinical status at Days 8, 15, 22, and 28 between pacritinib + SOC versus placebo + SOC
6. To compare the rate of use of immunomodulatory agents as treatment for COVID-19 during the 28 days following randomization between pacritinib + SOC versus placebo + SOC
7. To evaluate the toxicity profile of pacritinib therapy in hospitalized patients with severe COVID-19 with or without cancer

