### **7.2.4 Prior and Concomitant Medications**

Concomitant medications will be collected from the time of consent through 30 days following the last dose of pacritinib/placebo.

Prior medications are medications that were started and stopped prior to the first dose of study drug. Concomitant medications are medications that were taken on or after the first dose of study drug. Recorded prior and concomitant medications will be coded using the WHO Drug Dictionary (version March 2020 or later as specified in the Data Management Plan).

Recorded concomitant medications will be summarized by Anatomical Therapeutic Chemical (ATC) levels and PT. Concomitant medications of special interest (e.g. immunomodulatory agents/antiviral) will be summarized separately. A patient will be counted only once within each ATC level and PT but may contribute to more than one PT within an ATC.

Prior and concomitant medications as well as concomitant medications of special interest (immunomodulatory agents/ antiviral) will be listed.

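### The immunomodulatory-use rate counts listed agents begun before randomization and use for other diseases, which dilutes the tested comparison between arms.

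*SAP*

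**What the plan says.** The aim in SAP 2.2, objective 6, is "To compare the rate of use of immunomodulatory agents as treatment for COVID-19 during the 28 days following randomization". Protocol 11.1.1 defines the endpoint with the same restriction to COVID-19 treatment, and SAP 6.2.5 opens with it too.

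The derivation in SAP 6.2.5 then drops the restriction. A patient counts "if any medication used by the patient between Day 1 and Day 28 is coded to the list of preferred names in" Appendix 1, divided by the ITT population. SAP 7.4.2.5 compares this rate between arms with a stratified CMH test.

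Four other places decide what the rule captures:

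- SAP 7.2.4: "Prior medications are medications that were started and stopped prior to the first dose of study drug". By contrast, "Concomitant medications are medications that were taken on or after the first dose of study drug". A drug begun earlier and continued past the first dose therefore falls in the second group.
- Protocol 6.6: "Hydroxychloroquine, chloroquine, azithromycin, corticosteroids, and antiviral agents are permitted concomitant medications".
- Protocol 4.1.2, criterion 20, excludes "Administration of an IL-1 or IL-6 blocking immunomodulatory agent (such as tocilizumab, canakinumab, sarilumab, anakinra) within 48 hours prior to randomization". Criterion 17 separately excludes recent JAK2 inhibitors. No criterion excludes corticosteroids.
- Protocol 4.1.1 requires "Provision of informed consent within 96 hours after hospitalization", so several days of hospital treatment may precede randomization.

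The corticosteroid row of SAP Table 8 reads "Decadron, Dexamethason, Hydrocortisone, Metholprednisolne, Prednisone, Solumedrol". SAP 9 declares no change from the protocol-specified analysis.

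**The concern.** A patient who has been on dexamethasone since admission and is still on it at the first dose is a user on Day 1, whatever study drug does afterwards. If that patient later deteriorates and starts tocilizumab, the binary score does not change. A patient on long-term prednisone for an unrelated disease is also a user.

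Use fixed before randomization should be balanced between arms on average, but it cannot respond to treatment. Every such patient adds to both rates and contributes nothing to the difference. The formal test loses sensitivity as background use grows, and a null result would say little about whether pacritinib changed the use of further immunomodulation.

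The missing indication is a separate matter. There the derivation departs from the endpoint that the protocol and the SAP both state.

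**Working it through.** **The plan's own figure.** The documents give no rate, effect or power for this endpoint. Their only sample-size figure, about 200 patients, belongs to the primary endpoint (13.5% versus 26.5%, 80% power, one-sided 0.10). The pooled-variance formula gives 85 per arm. The continuity correction n/4 × [1 + √(1 + 4/(n × 0.13))]² raises this to 100 per arm, or 200 in total. The figure reproduces, and it supplies the 100 per arm used below.

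**Inputs.**
- n = 100 per arm (SAP 3.4).
- Assumed: new starts after randomization of 40% on placebo and 20% on pacritinib, independent of baseline use.
- Assumed: a share b of each arm is already on a listed agent at randomization and still on it on Day 1. The documents give no value, so a range is shown.
- Significance level: none is stated for this test. Two-sided 0.05 matches the planned 95% intervals; one-sided 0.10 is the level given for the primary endpoint. Both are shown.

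**Dilution.** Under the SAP 6.2.5 rule, each arm's rate is b + (1 − b) × (new-start rate). Subtracting one arm from the other cancels b, so the tested difference is (1 − b) × (40% − 20%).

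**Power.** I use an unstratified two-proportion approximation to the CMH test: Φ[(d − z × SE0)/SE1], with SE0 pooled under the null and SE1 unpooled.

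Example at b = 0.5:
- Rates are 0.5 + 0.5 × 0.4 = 70% and 0.5 + 0.5 × 0.2 = 60%, so d = 0.10.
- SE0 = √(2 × 0.65 × 0.35/100) = 0.0675.
- SE1 = √(0.70 × 0.30/100 + 0.60 × 0.40/100) = 0.0671.
- Two-sided 0.05: (0.10 − 1.96 × 0.0675)/0.0671 = −0.48, power 32%.
- One-sided 0.10: (0.10 − 1.2816 × 0.0675)/0.0671 = 0.20, power 58%.

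| b | Rates as written (placebo vs pacritinib) | Difference (points) | Power, two-sided 0.05 | Power, one-sided 0.10 |
|---|---|---|---|---|
| 0 | 40% vs 20% | 20 | 88% | 97% |
| 0.2 | 52% vs 36% | 16 | 63% | 84% |
| 0.5 | 70% vs 60% | 10 | 32% | 58% |
| 0.8 | 88% vs 84% | 4 | 13% | 32% |
| 0.9 | 94% vs 92% | 2 | 8% | 23% |

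**What a new-start rule recovers.** If baseline users add a different listed agent at the same 40% versus 20%, power is 88% (two-sided 0.05) or 97% (one-sided 0.10) at every b. If they never add one, the rates become (1 − b) × 40% and (1 − b) × 20%:

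| b | New-start rates | Power, two-sided 0.05 | Power, one-sided 0.10 |
|---|---|---|---|
| 0.2 | 32% vs 16% | 76% | 92% |
| 0.5 | 20% vs 10% | 51% | 76% |
| 0.9 | 4% vs 2% | 13% | 33% |

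Both limits are above the power of the current rule at the same b.

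**The case against.** The best defence is that the SAP measures what the protocol asks for. Objective 6 and the protocol endpoint speak of a rate of use, not of new or rescue use, so a new-start rate answers a different question. That stands, and it is why the any-use rate should be kept. It does not defend the omitted indication, which the protocol does require.

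A reader might infer three stronger things that the documents do not support:

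- **That background use saturates the endpoint.** In the illustration, near-saturation needs b of about 0.8 or more. No section gives b, and Protocol 1.1.2 describes care as mainly supportive.
- **That escalation is invisible.** SAP 7.2.4 commits to summarizing concomitant medications by preferred term, with immunomodulatory agents summarized separately. SAP 7.4.2.5 adds the number of agents per patient and a by-patient listing. Because recent IL-1 and IL-6 blockers are excluded at entry, tocilizumab and anakinra in those tables will mostly be new starts. Still, these outputs are descriptive, do not separate new from baseline use in general, and leave the CMH-tested binary unchanged.
- **That the comparison is biased.** Randomization makes pre-existing use a source of dilution, not of systematic difference between arms.

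It is also fair to say that this is one of six secondary efficacy endpoints in a Phase 2 trial, with no alpha allocation or decision rule attached. That limits the consequence; it does not remove the defect.

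**Conclusion.** The point holds in a limited form. The tested rate mixes use that study drug could affect with use that it could not, and its derivation omits the COVID-19 indication stated in the objective, in the protocol endpoint and at the start of SAP 6.2.5 itself.

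The loss of a fraction b of the difference follows from the rule for any b above zero, given equal b in both arms. The power figures depend on the assumed 40% versus 20%, on independence from baseline use, and on the significance level. At b = 0.2 the loss is 25 points of power at two-sided 0.05 (88% to 63%) and 13 points at one-sided 0.10 (97% to 84%), so it matters well before any ceiling.

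It would go too far to say that the endpoint cannot answer objective 6. It answers a question about overall use, with sensitivity that falls as background use rises. The change should be made because it is cheap and the endpoint carries a formal test.

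**What to change.** In SAP 6.2.5 and 7.4.2.5:

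1. Apply the COVID-19 indication in the derivation.
2. Run the CMH comparison on the proportion of ITT patients who start, after randomization and through Day 28, a listed agent that they were not receiving at randomization. A different listed class added to a baseline agent counts. Anchor the window on randomization, because SAP 7.1.1 sets Day 1 at the first dose and allows randomization to come before it.
3. Keep the protocol-worded rate of any use as treatment for COVID-19 alongside it.
4. Report use of listed agents at baseline by arm.
5. Record the change in SAP 9.

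The cost is SAP wording and a derivation from the concomitant-medication records. The downsides are fewer events, reliance on the recorded start date and indication, and only partial recovery of power if baseline users seldom add another agent (51% at b = 0.5, two-sided 0.05, if they never do). The documents do not show whether the case report form captures both items for every medication; that should be confirmed first.

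### The closed drug list that defines secondary endpoint 6 omits eculizumab, which the endpoint names, and counts remdesivir, which no endpoint text names

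*SAP*

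**What the plan says.** Protocol 11.1.1, secondary endpoint 6, defines the rate as "the proportion of patients reporting use of medications such as corticosteroids, tocilizumab, anakinra, or eculizumab as treatment for COVID-19", over the 28 days after randomization. SAP 6.2.5 opens with the same purpose and the same four examples: agents "such as corticosteroids, tocilizumab, anakinra, or eculizumab, will be assessed as a secondary endpoint".

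The rule that does the counting comes next. A patient is a user if "any medication used by the patient between Day 1 and Day 28 is coded to the list of preferred names in" Appendix 1, and the formula divides the number of such patients by the ITT total. Appendix 1 makes the list exclusive: "Immunomodulatory agent usage will be identified based on concomitant medications that are classified according to the following WHODD preferred names". Table 8 has four rows: six corticosteroid names; tocilizumab as the only IL-6 inhibitor; anakinra as the only IL-1 inhibitor; and remdesivir, under the label "Antiretrovirals".

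Protocol 6.6 bears on what belongs in the class: "The use of IL-1 or IL-6 blocking immunomodulatory agents (such as tocilizumab, canakinumab, sarilumab, anakinra) is allowed" when a patient is clinically deteriorating, and study drug must then be stopped.

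Protocol 11.3 and SAP 7.4.2.5 compare the rate between arms with a stratified CMH test. SAP 7.4.2.5 also plans a summary of the number of agents per patient and, optionally, summaries by Table 8 category and by preferred term. SAP Section 9 states that nothing departs from the protocol-specified analysis.

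**The concern.** An endpoint is what its counting rule counts. Here the descriptive text and the operative list disagree on named drugs. A patient whose only agent is eculizumab meets the endpoint as the protocol words it but is classed as a non-user. A patient whose only listed drug is remdesivir is classed as an immunomodulator user, although no endpoint text mentions an antiviral. A programmer who follows Appendix 1 exactly will produce a rate that is not the protocol's rate, and Section 9 gives no sign that this was intended.

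What is at stake is one tested secondary comparison and one planned descriptive count. IL-1/IL-6 blockers are given on deterioration and end study treatment, so their use is the kind of event this endpoint exists to show. The primary endpoint does not use Table 8.

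**Working it through.** **Term-by-term comparison**

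| Drug | Named in endpoint 6 (protocol 11.1.1, SAP 6.2.5) | In Table 8 |
|---|---|---|
| Corticosteroids | Yes | Yes (six names) |
| Tocilizumab | Yes | Yes |
| Anakinra | Yes | Yes |
| Eculizumab | Yes | **No** |
| Sarilumab, canakinumab | No; cited as IL-1/IL-6 blockers in protocol 4.1.2 (criterion 20) and 6.6 | No |
| Remdesivir | No | **Yes** |

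The two bold entries are direct conflicts. Sarilumab and canakinumab are class omissions: they enter the endpoint only through its open wording and the protocol's own examples of the class. The COVID-19 condition stands in the opening sentence of SAP 6.2.5 and in 7.4.2.5, but not in the counting sentence or the formula.

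**Possible size**

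The plan gives no usage rate, significance level or power for this endpoint, so there is no figure of its own to reproduce. Everything below rests on assumed ranges. With about 100 patients per arm, one percentage point is about one patient.

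*Omitted agents.* Let u be the share of an arm that takes an omitted agent and c the share of those who also take a Table 8 drug and so are counted anyway. The rate is understated by u(1 − c).

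| u | c = 0% | c = 50% | c = 90% |
|---|---|---|---|
| 0% | 0 | 0 | 0 |
| 1% | 1.0 | 0.5 | 0.1 |
| 5% | 5.0 | 2.5 | 0.5 |
| 10% | 10.0 | 5.0 | 1.0 |

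(percentage points)

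*Remdesivir.* Let p be the true share of users and r the share of non-users who receive remdesivir. The counted rate is p + r(1 − p), so the overstatement is r(1 − p). At r = 50% this is 25, 12.5, 5 and 2.5 points for p = 50%, 75%, 90% and 95%.

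*Difference between arms.* If r is the same in both arms, the true difference is multiplied by (1 − r). True rates of 60% and 75% (15 points apart) are counted as:
- r = 20%: 68% and 80%, 12 points apart
- r = 50%: 80% and 87.5%, 7.5 points apart
- r = 80%: 92% and 95%, 3 points apart

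True rates of 90% and 95% (5 points apart) give 4, 2.5 and 1 points. If r differs between arms, shrinkage is no longer assured. With p = 60% in both arms and r = 20% against 50%, the counted rates are 60 + 0.2 × 40 = 68% and 60 + 0.5 × 40 = 80%, a 12-point difference where none exists.

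*Net any-use error in one arm.* This is the remdesivir-only share minus the omitted-only share: 1% − 5% = −4 points, or 10% − 5% = +5 points. The sign depends on the inputs.

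*Agents per patient.* If R is the share of the arm on remdesivir and each affected patient takes one omitted agent, the mean is off by R − u. At u = 5% and R = 20%, 50%, 80% that is +0.15, +0.45 and +0.75. It is zero when R = u.

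Corticosteroids given for another condition would add to the overcount if the counting sentence is read alone; the documents give no basis for bounding that amount.

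**The case against.** Several counter-arguments have force.

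- The endpoint's examples are illustrative and the protocol leaves analysis detail to the SAP, so a list that omits sarilumab and canakinumab does not contradict the endpoint as written. That is right, and they rank below eculizumab here. The argument does not rescue eculizumab, which is one of the named examples in both documents.
- A reader might infer that the SAP abandons the COVID-19 condition. It does not. The phrase opens SAP 6.2.5 and returns in 7.4.2.5, and the counting sentence can be read within that scope. What remains is an operative rule and formula that do not state it.
- Protocol 6.6 might be cited to show that antivirals are a separate class: "Hydroxychloroquine, chloroquine, azithromycin, corticosteroids, and antiviral agents are permitted concomitant medications". That sentence puts corticosteroids, which the endpoint names, in the same list as antivirals. It sorts drugs by permission and does not settle what the endpoint excludes. SAP 7.2.4, which mentions immunomodulatory agents and antivirals together as medications of special interest, can be read as one group or two. The case against remdesivir is simpler: no endpoint text names it or any antiviral.
- A reader might infer that the category summary is wrong whenever remdesivir is used. Remdesivir has its own row, so the corticosteroid, IL-6 and IL-1 rows are unaffected and the fault there is one of labelling. The optional preferred-term summary would show remdesivir openly. The separate summary in SAP 7.2.4 is not tied to Appendix 1 and may show omitted drugs too. None of these displays corrects the tested rate.
- The magnitudes rest on assumed usage. That stands: if no patient receives an omitted agent, the omission has no effect, and if nearly every patient receives a listed corticosteroid for COVID-19, the any-use rate barely moves.

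**Conclusion.** The mismatch holds as a matter of text. A closed list leaves out a drug the endpoint names and includes one that no endpoint text names, while the SAP declares no change from protocol. The missing IL-1/IL-6 blockers and the unstated condition in the counting sentence are secondary.

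The consequence is limited to the tested any-use rate and the agents-per-patient count for one secondary endpoint. It is tempting to conclude that the list biases the comparison in a known direction, or that counting remdesivir will hide a treatment effect. The documents do not support either. Omissions lower the count, remdesivir raises it, and dilution by (1 − r) requires equal remdesivir use among non-users in both arms. Neither size nor direction can be determined without usage data, and the any-use error is small if affected patients also take a listed corticosteroid. The primary analysis is unaffected. Severity is minor. Confidence is high for the eculizumab and remdesivir mismatch and lower for how much it would change a result.

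**What to change.** Before unblinding:

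1. In SAP Appendix 1 Table 8, add a row for eculizumab. For class consistency, add sarilumab to the IL-6 row and canakinumab to the IL-1 row.
2. Remove remdesivir from the endpoint 6 count and report it separately as an antiviral. If counting it is intended, declare that in SAP Section 9 as a change from protocol endpoint 6.
3. In the counting sentence of SAP 6.2.5, insert *as treatment for COVID-19* after the words about medication used by the patient. Apply it from the recorded indication or, if none is recorded, by blinded medical review of the listed-drug records.
4. While editing, correct the title of Table 8 ("MedDRA Preferred Term List for Immunomodulatory Agents"), since Appendix 1 says the names come from the WHO drug dictionary.

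The cost is one new row, two added names, one name removed or declared, and a short phrase. Concomitant medications are already collected and coded, so no new drug-use data are needed. The only real work is the blinded review; whether it is needed depends on whether the CRF captures the reason for use, which the documents do not say. Acting before unblinding also avoids a corrected analysis that SAP Section 1 would require to be labelled post hoc.
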